6.2.7 Day 28 (± 3 days) (D) Delete: Serum HGF Delete: VM202 DNA levels Delete: Anti-HGF Antibodies	22	Deleted laboratory test
6.2.8 Day 59 (± 7 days) (C)	22	Change due to

Formerly: VM202 DNA levels Modified to: VM202 DNA levels (If DNA is detected at Day 21)		deleted laboratory tests on Day 21
6.2.13 Unscheduled Visits (D) Delete: Serum HGF levels Delete: VM202 levels (if visit is before Day 59)	25	Deleted laboratory test
6.2.14 Early Termination Visits (D) Delete: Serum HGF levels Delete: VM202 levels	26	Deleted laboratory test
9.4 Data Safety Monitoring Committee (C) Formerly: A Data Safety Monitoring Committee will review all safety data after each cohort of 3 subjects has completed the 30-day follow-up period after the first dose of study drug has been administered.	43	The cumulative safety of VM202 demonstrated in the first 2 cohorts allows advancement to
Modified to: A Data Safety Monitoring Committee will review all safety data available 30 days after the first subject in each cohort is dosed and subsequent to day 15 dosing of the other 2 subjects in the same cohort.		future cohorts in a prudent and expeditious timeframe.
Version 6.0 Modifications		
Signature Page (C) Formerly: Version Number: 5.0 Date: November 29, 2007	ii	Changed amended version number and date.
Modified to: Amended Version Number: 6.0 Date: August 31, 2009		
Global Protocol Change - Study Duration Formerly: 19 month plus 4 year follow-up after Day 365	xi, xii,xiv,8, 12, 26	Changed due to no indication of long term persistence of plasmid in nontarget tissues and no evidence of off-target angiogenesis in any of our preclinical and clinical studies of VM202 to date.
Modified to: 30 months	xi	This is the actual

		study duration
6.2.12 Long Term Follow-Up	27	
Add: Reason for hospitalizations, if applicable		Added to clarify
		hospitalization question on CRF.

Reference

- ² Taniyama Y, Tachibana K, Hiraoka K, et al. Development of safe and efficient novel nonviral gene transfer using ultrasound: enhancement of transfection efficiency of naked plasmid DNA in skeletal muscle. Gene Therapy 2002;9(6):372-80.

FDA Food and Drug Administration

G gram(s)

GCP Good Clinical Practices HGF hepatocyte growth factor

IBC Institutional Biosafety Committee

ICH International Conference on Harmonisation IDUR investigational drug utilization record

IND Investigational New Drug
INR international normalized ratio
IRB Institutional Review Board

IV intravenous

IVRS Interactive Voice Response System

Kg kilogram(s)

LOCF last observation carried forward

LIST OF ABBREVIATIONS (CONTINUED)

LV left ventricular Mg milligram(s) Min minute(s)

mmHg millimeters mercury

MRA magnetic resonance angiography

MTD maximum tolerated dose

N number Ng nanogram(s)

NIH National Institutes of Health NYHA New York Heart Association

 O_2 oxygen

OBA Office of Biotechnology Activities

PAD peripheral artery disease
pH hydrogen ion concentration
PHI protected health information

PPG photoplethysmograph

PTA percutaneous transluminal angioplasty

QD once daily
RBC red blood count
SAE serious adverse event
SAP Statistical Analysis Plan

sDBP sitting diastolic blood pressure

SE standard error

SGPT serum glutamic pyruvic transaminase (same as ALT)

SOC System Organ Class

SVR systemic vascular resistance

t_{1/2} elimination half-life

time of occurrence for maximum (peak) drug concentration

TBI toe-brachial index

TcPO₂ Transcutaneous Oxygen Pressure Assessment

VAS visual analog scale

VEGF vascular endothelial growth factor

vs. versus

WBC white blood count

WHO World Health Organization

DEFINITIONS

Adverse Event An adverse event (AE) is the development of an undesirable

medical condition following or during exposure to a

pharmaceutical product, whether or not considered causally

related to the product.

Baseline The last non-missing value prior to first dose of study drug. Serious AE An AE occurring at any dose that: results in death; is a

life-threatening experience; requires hospitalization or prolongation of an existing hospitalization; results in a persistent or significant disability/incapacity; or is a

congenital anomaly/birth defect in the offspring of a subject

who received study drug.

Treatment-emergent AE AEs with an onset time after the initial dose of study drug.

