8.0 Adverse Events and Serious Adverse Events

8.1 Adverse Event Definition

An AE is the development of an undesirable medical condition or the deterioration of a pre-existing medical condition following or during exposure to a pharmaceutical product, whether or not considered causally related to the product. AEs will be graded according to the National Cancer Institute's Common Terminology for Adverse Events v3.0 criteria.

An undesirable medical condition can be symptoms (e.g., nausea, chest pain), signs (e.g., tachycardia, enlarged liver) or abnormal results of an investigation (e.g., laboratory findings, electrocardiogram).

Therefore, an AE would include the following:

- Any event that is new (i.e., was not seen prior to the start of the study).
- A condition detected or diagnosed after the trial medication administration, even though it may have been present prior to the start of the study.
- A pre-existing intermittent event or condition that recurs with increased intensity and/or frequency after the start of the study.
- A pre- or post-treatment event that results from study participation (i.e., invasive procedures, modification of subject's therapeutic regimen)
- A change in blood pressure or heart rate that results in discontinuation of dosage or that exceeds protocol-specified criteria

An AE does not include the following:

- The disease or disorder being studied, or a sign or symptom of that disease or disorder, unless it is more severe than expected for the subject's condition.
- An overdose of the study medication if the subject is asymptomatic.
- A medical or surgical procedure (e.g., surgery, endoscopy, tooth extraction).
 Depending on the trial design, such a procedure may be the result of an AE or may result in an AE, but is not an AE itself.
- A pre-existing condition or disease that does not worsen following study drug administration.
- Hospitalization for elective surgery for a pre-existing disease or condition that did not worsen or for cosmetic surgery.

In this study an AE can include an undesirable medical condition occurring at any time after screening procedures have been started until the final follow-up visit, even if no study treatment has been administered.

When an adverse event occurs, the Investigator must:

- 1. assess whether or not the test article caused the AE;
- 2. determine the intensity of the AE;
- 3. record the action taken regarding the test article;

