8.2 Definition of an SAE

For each AE, you must determine if it is a serious adverse event (SAE) according to the following definition.

An SAE is an AE, occurring at any dose, which fulfills one or more of the following criteria:

- An event that results in death.
- An event that is immediately life threatening. This does not include an event that, had it occurred in a more serious form, might have caused death.
- An event that results in persistent or significant disability or incapacity.
- An event that is a congenital abnormality/birth defect
- An event that requires in-subject hospitalization or prolongs an existing
 hospitalization. Complications that occur during hospitalization and do not meet
 at least one of the above criteria for seriousness are AEs, not SAEs.
 Hospitalization means that the subject was formally admitted to the hospital, and
 does not include presentation at an emergency room.
- An event that, though not included in the above list, is an important medical event that may jeopardize the safety of the subject or may require medical or surgical intervention to prevent one of the outcomes listed above.

Medical and scientific judgment will be exercised in deciding whether a case is serious in those situations where important medical events may not be immediately life threatening or result in death, hospitalization, disability or incapacity. These include events that may jeopardize the subject or may require medical or surgical intervention to prevent one or

more outcomes listed in the definition of serious. Such events will usually be considered as serious. Examples of such events are:

- Angioedema not severe enough to require intubation but requiring intravenous hydrocortisone treatment
- Hepatotoxicity caused by paracetamol (acetaminophen) overdose requiring treatment with N-acetylcysteine
- Intensive treatment at the study site, in an emergency room, or at home for allergic bronchospasm
- Blood dyscrasias (e.g., neutropenia or anemia requiring blood transfusion) or convulsions that do not result in hospitalization
- Development of drug dependency or drug abuse (e.g., analgesics).

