8.4 Detection of AEs and SAEs: Method, Frequency, and Time Period

The methods of detection for AEs and SAEs include, but are not limited to, the use of non-leading verbal questioning of the subject (e.g., how do you feel?), clinical observation by the Investigator or study staff, physical examinations, monitoring of vital signs, or laboratory assessments.

AEs will be recorded for each subject from the time the subject signs the informed consent form through the subject's final follow-up visit. AEs and SAEs that result from study participation and occur prior to the start of the study drug will be recorded.

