10.2 Adverse Events

All adverse event summaries will be restricted to Treatment Emergent Adverse Events (TEAE), which are defined as those AEs that occurred after dosing and those existing AEs that worsened during the study. Verbatim terms on case report forms will be mapped to preferred terms and system organ classes using the MedDRA dictionary (version 9.1).

Each adverse event summary will be displayed by dose cohort. Summaries that are displayed by system organ class and preferred terms will be ordered by descending order of incidence of system organ class and preferred term within each system organ class. Summaries of the following types will be presented:

- Subject incidence of TEAEs and total number of unique TEAEs by MedDRA system organ class and preferred term;
- Subject incidence of TEAEs by MedDRA system organ class, preferred term, and highest severity. At each level of subject summarization a subject is classified according to the highest severity if the subject reported one or more events. AEs with missing severity will be considered severe for this summary;

- Subject incidence of TEAEs by MedDRA system organ class, preferred term, and closest relationship to study drug (Related/Not Related). At each level of subject summarization a subject is classified according to the closest relationship if the subject reported one or more events. AEs with a missing relationship will be considered related for this summary;
- Subject incidence of serious TEAEs and total number of unique serious TEAEs by MedDRA system organ class and preferred term.

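### The SAP states two different rules for treatment-emergent adverse events, and its definitions list omits parts of the protocol's AE and SAE definitions

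*SAP*

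**What the plan says.** **Treatment-emergent.** The SAP defines the term twice. The definitions list at the front requires "AEs with an onset time after the initial dose of study drug". SAP 10.2 uses "those AEs that occurred after dosing and those existing AEs that worsened during the study". Nothing says which rule governs. SAP 10.2 also limits all AE summaries to treatment-emergent events; these are Tables 12 to 15.

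**Collection window.** Protocol 8.4 states that "AEs will be recorded for each subject from the time the subject signs the informed consent form", and protocol 6.2.1 allows screening up to 30 days before Day 1. AEs with onset before the first dose can therefore be in the database.

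**Adverse event.** Protocol 8.1 covers the development of an undesirable condition "or the deterioration of a pre-existing medical condition". The SAP definitions list keeps the first half and omits the second.

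**Serious adverse event.** Protocol 8.2 has six criteria. The sixth is "An event that, though not included in the above list, is an important medical event that may jeopardize the safety of the subject", or that may need intervention to prevent one of the other outcomes. The SAP definitions list has five and omits this one. Among the protocol's examples of the sixth criterion is "Intensive treatment at the study site, in an emergency room, or at home for allergic bronchospasm".

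**The concern.** Primary safety endpoint 1 in protocol 4.1.1 is the incidence of adverse events through Day 365, and Tables 12-15 are the only AE tables in the SAP. Protocol 9.0 makes the SAP the working record of the statistical evaluation, so its definitions are what a programmer would follow. With two rules and no order of precedence, two programmers could each comply with the SAP and produce different AE tables. The onset-only rule is also the wrong one for safety: it drops an event that was present before dosing and became worse after injection. The worsening clause in 10.2 has the opposite fault, since it does not say that the worsening must follow a dose.

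The omissions from the AE and SAE definitions raise a related question: whether an analyst who relied on the SAP's list would select fewer serious events than the investigator reported under the protocol.

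**Working it through.** There is no design figure to reproduce. The check applies the definitions to cases and then sizes one reclassification.

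**Step 1. Apply both treatment-emergent rules to the possible cases.**

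| Case | SAP definitions list | SAP 10.2 |
|---|---|---|
| A. AE starts after the first dose | in | in |
| B. AE starts between consent and first dose, never worsens | out | out |
| C. AE starts between consent and first dose, worsens after it | out | in |
| D. AE starts between consent and first dose, worsens only before it | out | in or out, depending on when the study is taken to start |
| E. Medical-history condition deteriorates after dosing, entered as an AE with post-dose onset | in | in |

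Case C is the firm disagreement. Case D is an ambiguity: the documents do not define the start of the study.

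**Step 2. Adverse event definition.** Protocol 8.1 and 8.3 both count worsening of something present earlier. The SAP definition does not mention it. Because the investigator records AEs under the protocol, the SAP wording removes an event only if someone screens recorded AEs against the SAP definition. No SAP text calls for that.

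**Step 3. Seriousness.** Both lists contain death, life-threatening event, hospitalization, disability and congenital anomaly: five shared criteria. The important medical event makes six in the protocol. Protocol 8.2 says an emergency-room visit is not hospitalization, so allergic bronchospasm treated there can be serious under the protocol's sixth criterion and meet none of the SAP's five. If it begins after the first dose it is Case A: it stays in Tables 12-14 whichever list is used, and only its place in Table 15 is open. SAP Appendix A takes the AE and SAE listings from the same CRF plate (97), so a selection step is needed, and the SAP does not say that it uses the investigator's assessment.

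**Step 4. Size of one reclassification.** Tables 12-15 are laid out by cohort. The shift from one subject is 1/n:
- cohort of 3: 1/3 = 33.3 percentage points (0% to 33.3%)
- cohort expanded to 6: 1/6 = 16.7 points
- all 12 subjects, for reference only: 1/12 = 8.3 points

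**Step 5. How often.** The documents give no rate. Purely as an illustration, assume that each subject independently has probability p of an event that the rules treat differently. The chance of at least one is 1 - (1 - p)^n:
- p = 5%: 1 - 0.95^3 = 14.3% in a cohort of 3; 1 - 0.95^12 = 46.0% in 12 subjects
- p = 30%: 1 - 0.70^3 = 65.7%; 1 - 0.70^12 = 98.6%

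The range is assumed, and the conclusion does not depend on it.

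**The case against.** The best defence is that little turns on this wording. SAP 10.2 is the section that specifies the tables, and it includes worsened events; Case C is lost only if the definitions list is programmed instead. Pre-dose AEs should also be few: protocol 7.1.1 treats new findings at the Baseline evaluation as medical history, and Table 4-1 schedules AE collection from Day 1 pre-dose. The investigator decides what is an AE and whether it is serious, using protocol 8.1 and 8.2, and the SAP analyses what the CRF holds. The analysis is descriptive, with no formal cohort comparisons. The SAP is not narrower in every item either: its wording on life-threatening events and hospitalization is looser than the protocol's.

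All of this stands as a limit on reach. It does not settle which treatment-emergent rule applies, and protocol 8.4 still allows Case C to occur.

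A reader might go further and infer any of three things that the documents do not support:
- *An allergic event treated in an emergency room could vanish from the primary result.* If it begins after the first dose it is treatment-emergent under both rules and stays in Tables 12-14.
- *Progression of pre-existing disease generally drops out.* Deterioration of a medical-history condition, entered with a post-dose onset, counts under both rules (Case E).
- *Dose-escalation decisions are exposed.* DLTs have their own definition and CRF recording in protocol 7.1.9, and the monitoring committee reviews all safety data under protocol 9.4.

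**Conclusion.** The concern holds in limited form. The SAP contains two treatment-emergent rules that give different AE tables for an AE that starts between consent and first dose and worsens after injection. Its 10.2 rule is also open to counting worsening before any dose. One such subject changes a cell in a three-subject cohort by 33.3 percentage points; how many there will be cannot be known from the documents.

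The omitted deterioration clause and seriousness criterion are real mismatches with the protocol, but conditional ones. They matter only if the SAP's definitions, and not the investigator's record, are used to select events. For an important medical event with post-dose onset, the effect would then be confined to the serious-event output.

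The by-subject AE listing shows the events whatever the treatment-emergent flag, because the restriction in 10.2 applies to summaries. This is a cheap correction to the derivation of the AE tables that should be made before programming. It does not put the trial's safety conclusions in doubt.

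**What to change.** 1. State one treatment-emergent definition in both SAP places: onset after the first dose, or present before the first dose and increased in severity after it.
2. In SAP 10.2, replace the words *during the study* with *after the first dose*.
3. Align the SAP's AE definition with protocol 8.1, including deterioration, and its SAE definition with all six criteria of protocol 8.2.
4. State that Table 15 is built from the investigator's seriousness assessment on the CRF and is not re-derived from the SAP list.

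The cost is a few lines of SAP text and one derivation rule. No new data should be needed, provided the AE page lets a post-dose increase in severity be identified; the CRF is not among the documents, so that should be confirmed when the rule is written.

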1. INTRODUCTION

This document outlines the statistical methods to be implemented during the analyses of data collected within the scope of ViroMed Co., Ltd. Protocol US 06-1-001 [A Phase I, Dose-Escalation, Single Center Study to Assess the Safety and Tolerability of VM202 in Subjects with Critical Limb Ischemia]. The purpose of this plan is to provide specific guidelines from which the analysis will proceed. Any deviations from these guidelines will be documented in the clinical study report (CSR).

2. OBJECTIVES

2.1 Primary Objective

The primary objective of this study is to evaluate the safety and tolerability of intramuscular VM202 as a vehicle for therapeutic angiogenesis in subjects with critical limb ischemia.

2.2 Secondary Objectives

The secondary objectives of the study will include the following exploratory evaluations:

- To investigate the effects of the intramuscular VM202 to improve pain at rest and/or to heal ischemic ulcers of the affected limb. The VAS assessment tool will be used for this evaluation:
- To evaluate the anatomic and physiological extent of collateral vessel development in subjects with critical limb ischemia as measured by MRA;
- To evaluate the change in serum HGF levels from Day 1 to Day 59;
- To evaluate the change in VM202 DNA levels from Day 1 to Day 59;
- To evaluate the immune response to HGF in subjects with CLI as measured by the change in anti-HGF antibodies from Day 1;
- To evaluate the ability of VM202 to stimulate endothelial progenitor cells as measured by the change in endothelial cell progenitor assay levels from screening to Day 59.

3. STUDY OVERVIEW

This is a prospective, dose-escalation single center study to evaluate the safety and tolerability of intramuscular VM202 in subjects with critical limb ischemia.

Subjects selected for this study will have critical limb ischemia that has not responded to standard therapy with symptoms including pain at rest or ischemic ulcers.

The study will consist of four (4) cohorts with a total of 3 subjects enrolled in each cohort to VM202. The cohorts will be based on the planned different amounts of VM202 to be given. Planned levels of VM202 to be administered (defining the 4 cohorts) are the following: 2 mg, 4 mg, 8 mg and 16 mg. For each dose cohort, VM202 will be administered as a local intramuscular injection in 2 divided doses with a 2-week interval between the injections. Preliminary efficacy (hemodynamic assessments), safety and tolerability will be evaluated at Baseline (screening) and at designated time points throughout the study.

After all subjects in the first dose cohort have completed the 30-day (± 2 days) follow-up visit following the 1st dose of study drug, an interim safety evaluation will be performed with the submission of safety data to the Data Safety Monitoring Committee (DSMC). If the DSMC recommends continuing the study, the second dose cohort will be treated. This process will be repeated between the second and third dose cohort and between the third and fourth dose cohort. All 4 dose cohorts will be followed for up to five years from the time of the first dose of study drug administration. If a dose limiting toxicity (DLT) is observed in one subject in any dose group, three additional subjects will be added to the dose cohort in which the toxicity was observed. If no additional DLTs are observed in the 6 subjects in this dose level, it will be considered the maximum tolerated dose (MTD). If a DLT occurs in 2/6 subjects, then the preceding dose level will be considered the MTD.

4. GENERAL ANALYSIS CONSIDERATIONS

The statistical analyses will be reported using summary tables, figures, and data listings. Continuous variables will be summarized with means, standard deviations, medians, minimums, and maximums. Categorical variables will be summarized by counts and by percentage of subjects in corresponding categories.

Individual subject data obtained from the case report forms (CRFs), pharmacokinetic/pharmacodynamic data, and any derived data will be presented by subject in data listings.

All analyses and tabulations will be performed using SAS® Version 8.2 or higher on a PC platform. Tables and listings will be presented in RTF format. Upon completion, all SAS® programs will be validated by an independent programmer. In addition, all program output will undergo a senior level statistical review. The validation process will be used to confirm that statistically valid methods have been implemented and that all data manipulations and calculations are accurate. Checks will be made to ensure accuracy, consistency with this plan, consistency within tables, and consistency between tables and

corresponding data listings. Upon completion of validation and quality review procedures, all documentation will be collected and filed by the project statistician or designee.

